9.4 Database management and quality control

This study will be using eCRFs and the designated CRO will review the data entered by investigational staff for completeness and accuracy. Electronic data queries stating the nature of the problem and requesting clarification will be created for discrepancies and missing values and sent to the investigational site via the EDC system. Designated investigator site staff are required to respond promptly to queries and to make any necessary changes to the data.

Concomitant treatments and prior medications entered into the database will be coded using the WHO Drug Reference List, which employs the Anatomical Therapeutic Chemical classification system. Medical history/current medical conditions and adverse events will be coded using the Medical dictionary for regulatory activities (MedDRA current version) terminology.

Data from the screening molecular analysis will be collected locally and entered directly onto the eCRF. Tissue samples for pathway activation confirmation will be analyzed centrally.

At the conclusion of the study, the occurrence of any protocol deviations will be determined. After this action has been completed and the data has been verified to be complete and accurate, the database will be declared locked and the data made available for data analysis. Authorization is required prior to making any database changes to locked data, by joint written agreement between the US Oncology Medical Affairs Franchise Head and the US Oncology Medical Affairs Franchise Vice President.

After database lock, the investigator will receive a CD-ROM or paper copies of the patient data for archiving at the investigational site.

10 Statistical methods and data analysis

All data except the primary efficacy variable clinical benefit rate will be analyzed by a designated CRO in collaboration with Novartis. The analysis of the clinical benefit rate will be performed by a separate CRO using the Bayesian adaptive design approach described in details in [Appendix R](#). Any data analysis carried out independently by the investigator should be submitted to Novartis before publication or presentation. The data from all centers that participate in this study will be combined in the final safety and efficacy analysis.

This trial will enroll patients from at 6 histologic groups:

- NSCLC - Squamous
- Ovarian
- Glioblastoma Multiforme
- Squamous Head and Neck
- Bladder
- Cholangiocarcinoma

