10.4.3 Evaluation of trial success and futility

The clinical benefit rate will be evaluated for futility and early success by comparing posterior quantities for the rate to pre-specified early stopping criteria. The evaluations are planned to occur after the first 30 patients have been dosed for at least 16 weeks or discontinued, then every 13 weeks thereafter.

Early futility

If there is less than 10% probability that the response rate in a group exceeds the historical rate R_g , then the group will stop enrollment early for futility. Formally, enrollment will stop early for futility if:

$$\Pr(\pi_g > R_g) < 0.10.$$

A group is only eligible for early stopping once a minimum of 10 patients has been evaluated for response in that group.

Early success

If there is at least 95% probability that the response rate in a group exceeds the historical rate, then the group will stop enrollment early for success. Formally, enrollment will stop early for success if:

$$\Pr(\pi_g > R_g) > 0.95.$$

A minimum of 15 subjects will need to be evaluated prior to declaring a group to be efficacious.

Final analysis

The final analysis will occur when both accrual and follow-up are complete for all subjects. If, at the completion of the trial, there is at least 90% probability that the response rate in a group exceeds the historical rate, then the group will be considered a success. Formally:

$$\Pr(\pi_g > R_g) > 0.90.$$

In addition, a group will be considered as “promising” if:

$$0.80 = \Pr(\pi_g > R_g) < 0.90.$$

The control rates R_g are shown in [Table 14-1 of Appendix R](#).

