14.3.3.3 Final analysis

In addition, recall the final analysis will occur when both accrual and follow-up are complete in all groups, or after the database lock for the primary CSR. If, at the completion of the trial, there is at least 80% probability that the response rate in a group exceeds the historical rate, then the group will be considered a success. Formally:

$$\Pr(\pi_g > R_g) > 0.80.$$

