Clinical Development & Medical Affairs

BGJ398

Protocol CBGJ398XUS04 / NCT02160041

Modular phase II study to link targeted therapy to patients with pathway activated tumors: Module 3 – BGJ398 for patients with FGFR genetic alterations

Statistical Analysis Plan (SAP)

Author: [REDACTED]

Document type: Statistical Analysis Plan

Document status: Final v2.0

Release date: 13Jul2017

Number of pages: 25

Property of Novartis
Confidential

May not be used, divulged, published or otherwise disclosed
without the consent of Novartis

Document History – Changes compared to previous version of SAP.

Version	Date	Changes
---------	------	---------

Table of Contents

1	Statistical methods planned in the protocol and determination of sample size	5
2	Statistical and analytical plans.....	5
2.1	Change in planned analyses from the protocol.....	7
3	Subjects and treatments	7
3.1	Analysis sets	7
3.2	Subject disposition.....	8
3.3	Study Treatment and other concomitant medications	9
4	Patient demographics and other baseline characteristics.....	9
5	Study treatment exposure and other medications	10
5.1	Study treatment	10
5.2	Prior and concomitant medications/non-drug therapies	11
6	Efficacy and PRO evaluation	11
6.1	Clinical Benefit Rate (CBR).....	11
6.2	Overall Response Rate (ORR).....	12
6.3	Progression Free Survival (PFS)	12
6.4	Overall Survival (OS).....	13
6.5	Clinical Benefit Rate by Gene Mutations	13
7	Safety evaluation	13
7.1	Adverse events.....	13
7.1.1	Specific safety event categories	14
7.2	Deaths	15
7.3	Vital signs	15
7.4	Laboratory evaluations	15
7.5	Other safety evaluations	16
8	Interim analyses.....	16
9	Determination of sample size	16
10	Bayesian Adaptive Design	18
10.1	Introduction.....	18
10.1.1	Primary Analysis	18
10.1.2	Trial Logistics	19
10.2	Statistical Modeling	19
10.2.1	Hierarchical Model with Clustering.....	20
10.3	Evaluation of Trial Success and Futility.....	21
10.3.1	Early Futility	21

10.3.2	Early Success	21
10.3.3	Final Analysis.....	21
10.4	Simulation.....	21
10.4.1	Assumptions	21
10.4.2	Results	22
10.5	Modeling Details	23
11	References	25

1 Statistical methods planned in the protocol and determination of sample size

The primary efficacy variable, clinical benefit rate, will be analyzed by a Novartis designated Contract Research Organization (CRO), [REDACTED]. Analysis details are provided in Appendix R of the protocol, which is also included in Section **Error! Reference source not found.** of this Statistical Analysis Plan (SAP).

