2.1 Change in planned analyses from the protocol

The protocol specifies that analyses are to be conducted by “patient group” which is formed by the types of cancer at study entry. That is, subjects with the same tumor type will be considered as in the same “patient group”. For efficacy analyses, with exception of the primary analysis of clinical benefit rate (i.e., summarized by ‘patient group’), other descriptive summaries in general will be produced overall for all BGJ-treated subjects. Separate summaries may be produced for those groups with at least 10 subjects. All subjects will be combined for any safety analyses.

In the event of a low response rate, DOR will only be listed, and not tabulated. Subjects who had no disease progression/death will be censored at last adequate tumor assessment on or before the discontinuation/completion of the study or data cut-off.

For determination of PFS events, due to tumor assessments post study treatment are not collected, deaths occurred more than 30 days post treatment without prior progressive disease/relapse of disease will not be considered as an event.

For vital signs, values will be descriptively summarized by nominal visit. Separate summaries of significant abnormalities will not be provided, but will be reflected in adverse events (AEs).

3 Subjects and treatments

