6.1 Clinical Benefit Rate (CBR)

Clinical benefit is determined by investigator assessment for each tumor assessment and is defined as responses of CR or PR or SD \geq 16 weeks. For subjects with TIO diagnosis without measureable/evaluable disease, the following criteria will be used to determine the assessment at 16 weeks:

- the tumor associated changes of metabolic parameters: plasma level of FGF23 < or =180 RU/mL; and inorganic phosphorous, calcium, and 1-25-dihydroxy vitamin D greater than the lower limit of normal (LLN) (20%); and
- without requirement of supplementation therapy for at least the preceding cycle of the 16 week assessment.

Subjects with TIO diagnosis, but having known underlying tumor/disease type, their tumor response summaries will be treated same as for subjects with the same underlying tumor type.

In addition to tumor-specific measurements (e.g., radiological assessment of tumor response for solid tumors), progressive disease will also be considered when it was indicated either as a reason based on clinical assessment for the study treatment discontinuation or as a cause of on-treatment death. CR and PR (for solid tumors) require a confirmation that is at least a minimum of 4 weeks after the initial observation of response. Subjects who had confirmed CR/PR or SD prior to 16 weeks, but discontinued prior to 16 weeks for reasons other than

progressive disease, will have their clinical benefit defined as non-evaluable; subjects who had confirmed CR/PR or SD prior to 16 weeks, but progressed prior to 16 weeks, will be considered as not achieving clinical benefit; subjects who had CR/PR/SD occurred prior to 16 weeks, but progressed at or after 16 weeks without evidence of CR/PR/SD at or after 16 weeks, will also be considered as not achieving clinical benefit. CBR will be analyzed by comparing achieved CBR with a historical control rate of each tumor type, and if there is at least 90% probability that the response rate in a tumor type exceeds the historical rate, then the tumor type will be considered a success; it will be considered as promising if the probability is between 80% and 90%. Details for the analyses of CBR are located in Section [Error! Reference source not found.](#)

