There is no plan for a formal interim analysis of safety or other secondary endpoints for this study. However, for publication or other purposes, interim data review of clean data will be performed as necessary. At these interim reviews, patient demographics/baseline characteristics, the primary and secondary endpoints as applicable, and all important safety endpoints will be summarized. No formal report will be issued for these interim data reviews.

9 Determination of sample size

The sample size was chosen by the usual criteria of obtaining adequate power for the alternative hypothesis of interest as shown in the protocol Tables 4.2 of Appendix R (same as Table 2 as shown below in Section 10.4.2). This hypothesis corresponds to a generally effective treatment across groups and incorporates variation in treatment effects to reflect the realistic expectation that treatment effects may differ by group. In this setting, analytical

power calculations are not possible, but the design was simulated to obtain the power of the study as shown in Section 10 below. The sample size shown (minimum of 10 for futility stopping, minimum of 15 for early success and maximum of 30 as group cap) achieve adequate power for the alternative hypothesis. The simulations included the expected variable accrual by simulating a Poisson process with expected accrual also shown in the protocol Appendix R (same as Section 10 below).

Given the exploratory nature of the study design, there is no power consideration for secondary objectives.

10 Bayesian Adaptive Design

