10.3.3 Final Analysis

In addition, recall the final analysis will occur when both accrual and follow-up are complete in all groups, or after the database lock for the primary CSR. If, at the completion of the trial, there is at least 90% probability that the response rate in a group exceeds the historical rate, then the group will be considered a success. Formally:

$$\Pr(\pi_g > R_g) > 0.90.$$

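### Final success is set at posterior probability 0.90 in protocol 10.4 and the SAP but at 0.80 in Appendix R, and the stated power belongs to the 0.80 rule

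*SAP*

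**What the plan says.** **Threshold 0.90.** Protocol 10.4.2 gives the rule as a formula, and 10.4.3 repeats it in words: "If, at the completion of the trial, there is at least 90% probability that the response rate in a group exceeds the historical rate", the group is a success. SAP 10.1.1 and 10.3.3 ("there is at least 90% probability that the response rate in a group exceeds the historical rate") and SAP 6.1 agree. Protocol 10.4.3 and SAP 6.1 add a lower tier. In SAP 6.1's words, "it will be considered as promising if the probability is between 80% and 90" per cent.

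**Threshold 0.80.** Protocol Appendix R 14.3.3.3 declares success if "there is at least 80% probability that the response rate in a group exceeds the historical rate", and 14.1.1.1 gives the same threshold as a formula. Appendix R has no promising tier.

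**How the texts are linked.** Protocol section 10 points to Appendix R: "The analysis of the clinical benefit rate will be performed by a separate CRO using the Bayesian adaptive design approach described in details in" that appendix. SAP section 1 says: "Analysis details are provided in Appendix R of the protocol, which is also included in Section" (the cross-reference that follows is unresolved; the copy is SAP section 10). SAP 2.1, "Change in planned analyses from the protocol", does not mention the threshold.

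**Operating characteristics.** SAP section 9 describes the Appendix R results table as "same as Table 2 as shown below in Section 10.4.2". Protocol 10.8 and SAP section 9 both rest their claim of adequate power on these simulations.

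**The concern.** This is the primary endpoint and the only planned hypothesis test. A cohort that finishes between 0.80 and 0.90 gets two different verdicts from current text, and neither document says which prevails. If the question is left open until the final analysis, it could be settled after the posterior probabilities are known. The verdict also has consequences: protocol 4.1.2, 7.1.4.3 and 10.5.2 let the sponsor drop survival follow-up and reduce secondary analyses to listings if the primary endpoint is not met.

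The second problem is the table. One set of success probabilities cannot describe both a 0.80 and a 0.90 rule. If the figures come from 0.80, the power offered for the 0.90 rule is too high, and the type I error shown is not that rule's either.

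**Working it through.** **1. Compare the tables.** Protocol Table 14-2 and SAP Table 2 each hold 8 cohorts × 4 scenarios × 2 accrual rates = 64 probabilities. All 64 are identical.

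**2. Stated scenario means (10 / 5 per cohort).**
- All effective: 7.358/8 = 0.920; 6.498/8 = 0.812
- Two effective: (0.786 + 0.758)/2 = 0.772; (0.587 + 0.579)/2 = 0.583
- Half effective: 3.341/4 = 0.835; 2.664/4 = 0.666
- Null: 1.155/8 = 0.144; 1.152/8 = 0.144

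**3. Inputs to the re-simulation.** These come from SAP 10.3 to 10.5 and the matching parts of Appendix R:
- the eight control rates and the scenario treatment rates;
- Poisson accrual with mean 10 or 5 per cohort over two years, cap 30, no dropout;
- first interim when 30 patients have 16 weeks on study, then every 13 weeks;
- futility below 0.10 with at least 10 evaluated, early success above 0.95 with at least 15.

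The model is logit(π_g) = θ_g + logit(R_g), with a Dirichlet process prior on the clustering (α = 2). Within a cluster, θ_g ~ N(μ, τ²), μ ~ N(0, 1.82) and τ² ~ IG(3, 0.5). The posterior Pr(θ_g > 0 | data) was found by exact summation over all partitions of the eight cohorts, with numerical integration over μ and τ.

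Three things were assumed: uniform arrivals over 104 weeks; separate μ and τ² for each cluster; and, because the documents do not say whether 1.82 is a standard deviation or a variance, both readings were run (3,000 and 2,000 trials per scenario).

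**4. Results with interims.** Each pair is 1.82 read as SD / as variance.

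| Scenario (mean over cohorts) | Per cohort | Stated | Rule 0.80 | Rule 0.90 |
|---|---|---|---|---|
| All effective, power | 10 | 0.920 | 0.930 / 0.920 | 0.842 / 0.823 |
| | 5 | 0.812 | 0.808 / 0.790 | 0.640 / 0.609 |
| Two effective, power | 10 | 0.772 | 0.764 / 0.762 | 0.582 / 0.581 |
| | 5 | 0.583 | 0.565 / 0.575 | 0.364 / 0.356 |
| Half effective, power | 10 | 0.835 | 0.835 / 0.828 | 0.679 / 0.666 |
| | 5 | 0.666 | 0.670 / 0.642 | 0.462 / 0.428 |
| Null, type I error | 10 | 0.144 | 0.146 / 0.145 | 0.057 / 0.057 |
| | 5 | 0.144 | 0.144 / 0.138 | 0.054 / 0.048 |
| Two effective, type I error in the rest | 10 | 0.221 | 0.221 / 0.220 | 0.096 / 0.099 |
| | 5 | 0.205 | 0.207 / 0.200 | 0.088 / 0.079 |
| Half effective, type I error in the rest | 10 | 0.304 | 0.299 / 0.283 | 0.151 / 0.140 |
| | 5 | 0.266 | 0.279 / 0.259 | 0.131 / 0.118 |

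**5. Which rule produced the table?** At 0.80 the largest gap from a stated mean is 1.8 points (SD reading: 0.583 − 0.565) or 2.4 points (variance reading: 0.666 − 0.642). At 0.90 the smallest gap is 7.8 points (0.920 − 0.842). Monte Carlo error is too small to explain this: for a single cohort the SE is at most √(0.25/3000) = 0.009 here, and √(0.25/1000) = 0.016 in the sponsor's 1,000-trial runs.

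**6. Size of the loss in power.** Two quantities should be kept apart.
- *Same trials, 0.80 to 0.90:* 8.8 to 20.8 points (SD reading) and 9.7 to 21.9 (variance reading), so roughly 9 to 22.
- *Stated minus recomputed at 0.90:* 7.8 to 21.9 and 9.7 to 23.7, so 8 to 24. This also carries the small mismatch seen at 0.80.

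**7. Sensitivity.** A final-analysis-only run of 5,000 trials per scenario gave drops of 9.0 to 22.2 points, with 0.80 results within 2.1 points of the table. The interims matter little because few cohorts reach 10 to 15 evaluated patients.

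**8. A wording point.** Protocol 10.8 and SAP section 9 describe the alternative as allowing effects to differ between groups. Its odds ratios are nearly constant: lung (0.71/0.29)/(0.45/0.55) = 2.99, and bladder (0.73/0.27)/(0.47/0.53) = 3.05, with the other six between them.

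**The case against.** The best defence is that the intended rule is fairly clear. Appendix R calls itself a framework for all modules built on eight example cohorts, whereas the study-specific protocol text and the later SAP use 0.90 and deliberately add a promising tier. That is probably how a reader would settle it. But no text gives the body precedence, and protocol section 10 directs the analysing CRO to Appendix R. The conflict stands.

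Several narrower objections have weight:
- Adequate power is claimed only for the generally effective alternative, and no numeric target is set. At 10 per cohort, 0.82–0.84 could still be called adequate. The weak figure is 0.61–0.64 at 5 per cohort. The larger losses arise in the mixed scenarios, where both documents already warn of reduced power.
- The statement that null type I error stays below 0.20 remains true at 0.90. It is loose, not false.
- The silence of SAP 2.1 is weak evidence, because the SAP agrees with protocol 10.4. The fairer criticism is of SAP section 1, which presents its section 10 as Appendix R although the threshold differs.
- The simulated cohorts are not this trial's six groups. Glioblastoma and cholangiocarcinoma have no control rate in Table 14-1.

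The study is signal-seeking, so modest power is tolerable, but that does not justify quoting one rule's power for another.

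**Conclusion.** The concern holds and should be fixed before the final analysis of clinical benefit rate. The threshold conflict and the identical tables are direct readings of current text. That the table was not re-run for 0.90 is an inference, but a strong one: the documented model returns the table at 0.80 and misses every scenario mean at 0.90, under either reading of the μ prior.

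Under the 0.90 rule, mean power is roughly 9 to 22 points lower on the same trials (8 to 24 against the stated figures). Null type I error is about 0.05–0.06, not 0.144. In the simulated scenarios 9% to 18% of cohorts finish between 0.80 and 0.90, where the verdicts differ. These sizes apply to the eight example cohorts and rest on the assumptions in step 3. The textual conflict rests on none of them.

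**What to change.** State one final success threshold everywhere. If 0.90 stands, change Appendix R 14.1.1.1 and 14.3.3.3 to 0.90 and carry the promising tier into Appendix R and SAP 10.3.3.

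Re-run the simulation at the chosen threshold and replace protocol Table 14-2 and SAP Table 2 with the sponsor's own output, not the figures above. State whether 1.82 is a variance or a standard deviation. Then revise the type I error sentence under both tables and the adequate-power statements in protocol 10.8 and SAP section 9 to match. Label the output as applying to the example cohorts unless it is re-run for this trial's six groups. Describe the alternative as a near-constant odds ratio of about 3.

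The cost is wording in the protocol appendix and the SAP and one simulation re-run. The stated power becomes less favourable if 0.90 is kept. No patients are added.

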10.4 Simulation

We evaluated type I error and power for each of the 8 possible groups under a variety of possible “truths” indicating various possible true underlying probabilities within each group.

10.4.1 Assumptions

Accrual – Two scenarios for the assumed two-year expected accrual are investigated: 1) 10 subjects per group and 2) 5 subjects per group. Note that these are averages, the actual number of available subjects is simulated as a Poisson distribution with the specified mean.

Also note that the group cap of 30 applies, and thus if the number of available subjects in a group exceeds 30, only the first 30 available subjects in that group will be enrolled in the study.

Dropouts – We assume no dropouts for the purpose of this simulation.

Control Rates – Table 1 shows the assumed control clinical benefit rates for each group.

Table 1 – Controlled CBR values used in the simulations	
Tumor Type	Assumed Control Rate (R_g)
Lung LSCL	0.45
Bladder	0.47
Breast	0.50
Colorectal	0.38
GIST	0.50
HNSCC	0.45
Ovarian	0.47
Sarcoma	0.40

We consider four possible scenarios, or possible “truths” in the simulation. These consisted of a null scenario (where the treatment has no effect for any group), an alternative scenario (where the treatment is effective in all groups), a scenario where the treatment was effective in two of the groups, and a scenario where the treatment was effective in half of the groups.

Treatment Rates - The treatment rates for each scenario are shown in the table below. Values identical to the control are shown in normal text, while values greater than the assumed control rate are shown in bold.

	Null	Alternative	Two	Half
Lung LSCL	0.45	0.71	0.45	0.45
Bladder	0.47	0.73	0.47	0.47
Breast	0.50	0.75	0.50	0.50
Colorectal	0.38	0.65	0.38	0.38
GIST	0.50	0.75	0.50	0.75
HNSCC	0.45	0.71	0.45	0.71
Ovarian	0.47	0.73	0.73	0.73
Sarcoma	0.40	0.67	0.67	0.67

Simulation Details – For each scenario we simulated 1000 trials. For each interim within each trial, we ran 50,000 MCMC iterations after a 1,000 MCMC iteration burnin.

